9.4. Vital Signs

9.4.1. Vital Sign Parameters

- Heart Rate (beats/min)
- Systolic Blood Pressure (SBP) (mmHg)
- Diastolic Blood Pressure (DBP) (mmHg)
- Respiratory rate (breaths/minute)
- Body Temperature (°C)

9.4.2. Biostatistical methods

All vital sign parameters will be summarized using descriptive statistics for each dose level and overall for all time points assessed, including change from baseline (last pre-dose value) for all post-dose assessments. Pre-dosing vital sign on Cycle 1, Day 1 will be used as baseline data. If the baseline value is missing, then the data from Screening will be used as baseline data.

9.5. Physical examination

9.5.1. Body Systems Assessed

- General Appearance
- Dermatologic
- HEENT (Head, Eyes, Ears, Nose and Throat)
- Respiratory
- Cardiovascular
- Musculoskeletal
- Gastrointestinal

- Abdomen/Pelvic
- Neurological
- Other

For abnormal result of physical examination:

- Abnormal NCS (Not Clinically Significant)
- Abnormal CS (Clinically Significant)

9.5.2.Biostatistical methods

Physical examination will be summarized by study visit and treatment cohort. The frequency counts and percentages of subjects with different physical examination results and their clinical significance (for abnormal) will be summarized.

By-subject data listings will be generated for the physical examination data, including the Investigator assessment of clinical significance for abnormal findings, for all time points assessed.

9.6.12-lead ECG

9.6.1.ECG Parameters

- Ventricular Rate (beats/min)
- PR interval (msec)
- QRS duration (msec)
- QT interval (msec)
- QTc interval (msec)
- RR interval (msec)
- Overall interpretation of 12-lead ECG:
 - Normal
 - Abnormal NCS (Not Clinically Significant)
 - Abnormal CS (Clinically Significant)

9.6.2.Biostatistical methods

Descriptive statistics will be calculated for ventricular rate, PR interval, QRS duration, QT interval, QTc interval, and RR interval, including change from baseline (last pre-dose value on Cycle 1, Day 1) for each dose level (cohort) for all time points assessed. If triplicate ECG parameters are available, the average of the triplicate ECG parameters will be used. Unscheduled visits will be excluded from summary tables. However, the findings from the unscheduled will be listed.

In addition, the overall interpretation of 12-lead ECG results will be classified using frequency counts and percentages for the categories of Normal, Abnormal - Not Clinically Significant (NCS) and Abnormal - Clinically Significant (CS) for each treatment group for all time points assessed.

All ECG data will be presented in the by-subject data listings.

10. Efficacy

Statistical methods for the efficacy analyses will be primarily descriptive in nature, due to small number of subjects enrolled. Each dose level (cohort) and overall group will be summarized separately. No formal statistical comparisons of SCB01A dose levels will be made.

Efficacy endpoints include in the analysis are DCR, PFS, and OS. Efficacy endpoints will be analyzed using the Full Analysis Set. For PFS and OS, if there is no event reported (progression or death), their survival functions can not be estimated. Thus, only simple descriptive statistics will be provided.

When confidence interval (CI) is estimated, both 90% CI and 95% CI will be provided for DCR. For other endpoints, only 95% CI will be provided.

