2.5. Randomization and Assignment of Subjects to Treatment Groups

This is an open label study, and no randomization is applicable.

3. Statistical Considerations

Data will be handled and processed according to the sponsor's representative (Novotech (Australia) Pty Ltd) Standard Operating Procedures (SOPs), which are written based on the principles of Good Clinical Practice (GCP).

All data collected on the eCRFs will be presented in the data listings and will be listed and sorted by subject number and visit, where applicable. All summaries will present the data by SCB01A dose level (cohort) and overall (total enrolled subjects), as applicable. Patient data will be separated via cohort and presented for enrolled subjects.

Unless otherwise stated, the following statistical approaches will be taken:

- Continuous variables: Descriptive statistics will include the number of non-missing values (N), mean, standard deviation (SD), median, minimum, maximum.
- Categorical variables: Descriptive statistics will include frequency counts and percentages per category. Percentages will be rounded to one decimal place, with the denominator being the number of subjects in the relevant population with non-missing data, unless otherwise specified.
- Imputation: No missing data will be imputed generally.
- Pharmacokinetic (PK) data: For PK data the arithmetic mean, standard deviation (SD), median, minimum, maximum, geometric mean and coefficient of variation (CV%) values will be presented.
- Confidence intervals (CIs): CIs will be two-sided and will use 95% confidence levels unless specified otherwise.
- Baseline: Baseline values will be defined as the last non-missing observation for each subject prior to the dosing of study medication (i.e. start of infusion on Cycle 1, Day 1).
- Repeat assessments: Repeat assessments will be included in summary presentations (Tables). Only the original values will be used in summary presentations. All repeat assessments captured in the Electronic Data Capture (EDC) system will be presented in the data listings.

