10.2. Progression-free Survival and Overall Survival

Progression-free Survival (PFS) is defined as the time from the start of treatment up to the date of first progression based on RECIST v1.1, second primary malignancy or death from any cause, whichever occurs first. Patients without progression or death will be censored at the last disease assessment date.

Overall survival (OS) is defined as the time from the start of treatment up to the date of death, regardless of causes. Patients without death will be censored at the last follow up date.

The analysis of PFS and OS is based on the survivor function, which is the probability to survive or, more generally, to stay event-free beyond a certain point in time. The survival function is estimated by the Kaplan-Meier method. The survival function will be summarized for 25th percentile, median, and 75th percentile and their 95% confidence intervals. For OS, survival rate at Week 36 will be reported, based on the survival function, if this estimate is available. The plot of Kaplan-Meier estimates for the dose levels will be presented. If there is no event reported (progression or death), only simple descriptive statistics will be provided.

11. Health Outcome and ECOG-PS

Statistical methods for the health outcome analyses will be primarily descriptive in nature. Each dose level (cohort) will be summarized separately. No formal statistical comparisons of SCB01A dose levels will be made.

Patients would complete the EORTC QLQ-C30 and QLQ-H&N35 questionnaires at screening and before study drug administered, except Cycle 1, Day1. The questionnaire consists of 65 questions that help determine the health outcome of the patients. Health outcome endpoints will be analyzed using the Full Analysis Set.

Analysis of Eastern Cooperative Oncology Group Performance Status (ECOG-PS) will be provided as well.

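### SAP sections 10 and 10.2 wrongly say that PFS and OS survival functions cannot be estimated without an event, which could drop the Week 36 OS rate for a group with no deaths (minor)

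*SAP*

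**What the plan says.** SAP section 10 (Efficacy) covers the case of no events: "For PFS and OS, if there is no event reported (progression or death), their survival functions can not be estimated". It continues: "Thus, only simple descriptive statistics will be provided". Section 10.2 says the same at its end: "If there is no event reported (progression or death), only simple descriptive statistics will be provided". Neither place says what those statistics are, or whether no event means none in a dose level or none in the study.

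Section 10.2 also sets out the regular analysis:

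- Estimator: "The survival function is estimated by the Kaplan-Meier method".
- Summaries: "The survival function will be summarized for 25th percentile, median, and 75th percentile and their 95% confidence intervals".
- Week 36: "For OS, survival rate at Week 36 will be reported, based on the survival function, if this estimate is available".
- OS censoring: "Patients without death will be censored at the last follow up date".

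SAP section 2.3 lists the Week 36 OS rate as an efficacy endpoint, defined as the percentage of subjects alive at that time. No fixed-time rate is planned for PFS. Section 1 reports that the study stopped in the run-in phase with five subjects enrolled. Section 2.1 says they were recruited to two dose levels, and section 10 has each dose level and the overall group summarised separately.

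**The concern.** The rule confuses a survival function that cannot be estimated with one that is flat. Kaplan-Meier needs subjects at risk, not events, to return a value.

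The error matters through one link. Section 10.2 makes the Week 36 OS rate depend on the survival function being available, and section 10 declares that function unavailable when there are no events. Taken together and read literally, they could remove a listed endpoint for a group in which nobody died, although the data support an estimate. Whether the rate is reported would then depend on the outcome itself, which a prespecified rule should avoid.

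**Working it through.** The plan gives no figure to reproduce here. The check applies the named estimator to the case that the rule describes.

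**Inputs.** From the SAP: Kaplan-Meier and censoring at last follow-up (section 10.2), Week 36 as the OS time point (section 2.3), five subjects (section 1), two dose levels (section 2.1). Week 36 is 36 × 7 = 252 days after first treatment. Assumed, because the documents do not give them: censoring times, group sizes and true Week 36 survival.

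**Step 1. The estimate with no events.** S(t) = Π(1 − dᵢ/nᵢ). With every dᵢ = 0, each factor is 1, so S(t) = 1.0 up to the longest follow-up.

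- Assumed censoring at 100, 150, 252, 260 and 300 days: S(t) = 1.0 to day 300, three at risk at day 252, Week 36 rate 100%.
- Assumed censoring at 30, 60, 90, 120 and 150 days: S(t) = 1.0 to day 150. Day 252 lies beyond follow-up, so the rate is not estimable by any method.

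**Step 2. What really is unavailable.** S(t) never falls to 0.75, 0.50 or 0.25, so none of the quartiles can be estimated. The Greenwood standard error is 0, so the usual interval collapses to a point.

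**Step 3. A usable interval.** For n of n subjects known to be alive at Week 36, the exact (Clopper-Pearson) two-sided 95% lower limit is 0.025^(1/n); the upper limit is 100%.

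| n | 95% lower limit |
|---|---|
| 1 | 2.5% |
| 2 | 15.8% |
| 3 | 29.2% |
| 4 | 39.8% |
| 5 | 47.8% |

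**Step 4. Dependence on the outcome.** Take an assumed group of two, with one subject followed beyond Week 36. If the other dies at Week 20, the SAP reports S(36) = 1 − 1/2 = 50%. If the other is instead censored alive at Week 20, the literal rule reports no rate, although Kaplan-Meier gives 100% with one at risk.

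**Step 5. How often the rule could apply to OS.** With true Week 36 survival s and full follow-up, P(no deaths by Week 36) = sⁿ.

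| Group size n | s = 20% | s = 70% |
|---|---|---|
| 2 | 4% | 49% |
| 3 | 0.8% | 34.3% |
| 5 (all) | 0.03% | 16.8% |

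Shorter follow-up makes no observed deaths more likely, but also makes it less likely that anyone is at risk at Week 36.

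**The case against.** The case for leaving the text alone has four parts.

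1. **The trigger is narrow.** The rule does not say that it works by dose level. Applied to all five subjects, it is unlikely to operate. The Kaplan-Meier figures for PFS and OS are marked for production in SAP section 20, in a list limited by the available data. That suggests, without proving it, that events were expected. This stands as a limit on likelihood. It does not make the statement correct.
2. **Little is lost.** The overall survival table (section 18) and the survival status listing (section 19) are both marked for production, so a reader can see who was alive and when. The Week 36 rate serves a Phase II objective, and Phase II enrolled nobody. Section 1 puts the focus on safety and makes efficacy analysis conditional on having enough subjects or events. This stands, and it is why the point is minor.
3. **Printing 100% for one subject at risk could mislead.** True if it stood alone: the exact lower limit for 1 of 1 is 2.5%. The answer is to show the number at risk and the interval, not to call the function inestimable.
4. **A fallback suits the quartiles.** Agreed. For PFS, where no fixed-time rate is planned, the quartiles are the only planned numerical summary of the survival function.

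A reader might go further and infer that the SAP would print a finite mean or median survival for a group in which nobody died. SAP section 3 does set this default for continuous variables: "Descriptive statistics will include the number of non-missing values (N), mean, standard deviation (SD), median, minimum, maximum". But that default holds only where nothing else is stated, and the same list gives counts and percentages for categorical variables. The fallback in sections 10 and 10.2 is undefined, and numbers of events or of subjects alive would fit it equally well. Section 10.2 also states censoring rules, so its authors do separate censored times from events. A misstated median is a possible reading, not what the SAP specifies.

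**Conclusion.** The statement in sections 10 and 10.2 is wrong and should be corrected; the severity is minor. With no events the Kaplan-Meier estimate is 1.0 to the longest follow-up.

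The one consequence that the text supports is conditional. The Week 36 OS rate could be dropped if a group has no deaths and at least one subject is followed to Week 36. Both conditions are needed, and the point concerns OS only. It rests on a literal reading of the availability clause together with the no-event rule. The probabilities above rest on assumed survival, assumed group sizes and full follow-up. No test depends on the rate, efficacy is descriptive, and only five subjects are involved.

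**What to change.** Replace the no-event statements in SAP sections 10 and 10.2 with text along these lines:

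> If a group has no events, the Kaplan-Meier estimate is 1.0 up to the longest follow-up, and quartiles are reported as not estimable. For OS, when at least one subject is followed to Week 36, the Week 36 rate is reported with the number at risk and an exact (Clopper-Pearson) 95% CI among subjects with known Week 36 status. Numbers of events and of censored subjects are shown. Any summary of censored times is labelled as follow-up time, not survival.

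State also that a group means each dose level and the overall total. A table footnote should say that the interval is based on subjects with known Week 36 status, since these may be fewer than the subjects behind the Kaplan-Meier estimate. Reverse Kaplan-Meier follow-up is optional with so few subjects.

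The cost is a short text replacement and one footnote. No new data are needed, and section 10.1 already plans exact intervals of this kind for the disease control rate.

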10.1. Tumor Response and Disease Control Rate

Tumor assessments were made based upon the RECIST criteria (Response Evaluation Criteria in Solid Tumors version 1.1). Tumor assessments were scheduled at baseline, and every 3 cycles prior to next cycle until progression of disease. For this analysis purpose, tumor response evaluation at Week 9 (Cycle 4, Day 1) or end of treatment/early termination will be pooled and used as the best overall response from start of dosing up to Week 9.

For the analysis of tumor response, a summary table presenting the number and proportion of responders (DC) and non-responders (non-DC) in each dose level, together with the two-sided 90% and 95% confidence intervals for response rates will be produced. The proportion and the corresponding 90% and 95% confidence interval for each of the response categories (CR, PR, SD, PD, and unevaluable) by dose level will also be presented. The confidence interval will be based on Pearson-Clopper exact CI.

The details of target lesions, non-target lesion, and new lesions (if any) will be listed for each subject.

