Endpoints:	
Primary endpoint:
 
 DCR, defined as; complete response (CR) + partial response (PR) + stable disease (SD) at Week 9, according to RECIST v1.1 criteria 
Secondary endpoints:
 
 PFS OS rate at 36 weeks after first treatment with SCB01A Safety: The safety endpoints used to achieve the secondary objectives of this study are: 
 Hematology, clinical chemistry, coagulation factors and urinalysis laboratory data changes AE/SAE incidence Physical examination results changes Vital sign changes Electrocardiogram (ECG) (including PR, QRS, QT, QTc, and RR intervals) results Health outcomes assessment using patient-reported EORTC QLQ-C30 and H&N35 questionnaires.
Criteria for Evaluation:	
Efficacy measurements:
 
Tumor Measurement:
 
Tumor response will be assessed by using computerized tomography (CT) or MRI scans according to RECIST v1.1 at baseline, and every 3 cycles prior to the next cycle until progression of the disease. For patients who meet DC criteria after the first 3 cycles of study treatment, additional radiological tumor assessments will be performed at Week 12. Scans must include brain, chest, abdomen, and pelvis. The imaging technique used at baseline should be used throughout the study.
 
Patients will be considered evaluable for DCR in this study if they fulfill the criteria for evaluation according to RECIST v1.1, i.e., those patients who undergo a baseline disease assessment within 4 weeks of treatment initiation, and who undergo at least 1 disease assessment on the study.
 
 DCR is defined as the percentage of patients who have achieved CR, PR and SD at a particular time point after first treatment, according

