Two phase I clinical studies were performed “A Phase 1 Dose Escalation Study of SCB01A in Subjects with Advanced Solid Tumors Who Have Failed Standard Therapy” and “Long-Term Compassionate Use Study for Continued Administration of SCB01A in Subjects Who Completed Treatment With SCB01A in the Previous Protocol #SCB01A-01” respectively. The phase I study demonstrated that SCB01A has encouraging safety and efficacy and support for further Phase II study. 33 subjects were enrolled in the study and 31 subjects completed the main treatment. Among the 31 subjects, 11 of them completed the extension treatment of SCB01A. Up to date, 5 subjects, two in main and extension period respectively, experienced 7 SUSAR events. (Including gastric ulcer bleeding, thrombocytopenia, cough, radiation recall dermatitis and thromboembolic event, Muscle weakness lower limb and Sepsis). In addition, 5 dose limiting toxicities and 61 adverse reactions were reported in this study.

The aim of this Phase II study with SCB01A is to determine the effect of SCB01A in patients with squamous cell carcinoma of head and neck who have failed previous platinum based therapies.

2. Study Objectives

2.1. Run-In Phase:

Primary Objective

To determine the optimal dose for 3 cycles of i.v. administration of SCB01A on Days 1 and 8 of each cycle in a 3-week cycle.

Secondary Objective:

To evaluate the safety and toxicity for 3 cycles of i.v. administration of SCB01A on Days 1 and 8 of each cycle in a 3-week cycle

2.2. Phase II:

Primary Objective:

To assess the disease control rate (DCR) at the end of the 9th week (3 cycles, each cycle consists of 21 days) after treatment with SCB01A, according to the Response Evaluation Criteria in Solid Tumors (RECIST) version 1.1.

Secondary Objectives

The secondary objectives of the study are listed below:

- To assess the overall survival rate at 36 weeks after treatment of SCB01A in patients with recurrent or metastatic squamous cell head and neck cancer who have previously been treated with platinum therapy.
- To assess the progression-free survival (PFS)
- To determine the recommended dose regimen of SCB01A for further investigation in different settings of head and neck squamous cell cancer.
- To assess the safety and toxicity profile of study treatment.
- To assess the PK profile of SCB01A of patients in the run-in phase.

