3.4. End of Treatment (EOT) Evaluation/Early Withdrawal

EOT visit should be conducted 21 ± 2 days after the last infusion. Early withdrawal visit should be conducted within 21 days after the patient receives the last dose of study treatment.

The following assessments will be performed at the EOT/early withdrawal visit:

- Physical examination
- Vital signs
- ECOG performance status
- AEs
- Concomitant medication
- 12-lead ECG
- Tumor assessment (radiological imaging)
- Urinalysis
- Laboratory tests (hematology, clinical chemistry and coagulation)
- EORTC QLQ-C30 and H&N35

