2.3. Study Endpoints

Safety

- Hematology, clinical chemistry, coagulation factors and urinalysis laboratory data changes
- AE/SAE incidence
- Physical examination results changes
- Vital sign changes
- Electrocardiogram (ECG) (including PR, QRS, QT, QTc, and RR intervals) results

Efficacy

- Disease Control Rate (DCR) is defined as the percentage of subjects who have achieved complete response (CR), partial response (PR) and stable disease (SD) at Week 9 after first treatment, according to RECIST v1.1.
- Progression-free Survival (PFS) is defined as the time from the start of treatment up to the date of first progression based on RECIST v1.1, second primary malignancy or death from any cause, whichever occurs first.
- Overall survival (OS) rate at Week 36 is defined as the percentage of subjects who are still alive at 36 weeks after first treatment with SCB01A.
- Health outcomes assessment using patient-reported EORTC QLQ-C30 and QLQ-H&N35 questionnaires.

Health outcomes assessment

- EORTC QLQ-C30
- EORTC QLQ-H&N35

Pharmacokinetic

PK concentration:

- Plasma concentration of SCB01A at the sampling time

PK parameters:

- AUC_{0-t} : area under the plasma concentration-time curve from time zero to time t
- $AUC_{0-\infty}$: plasma concentration-time curve from time zero to infinite time
- C_{max} : maximum plasma concentration
- T_{max} : maximum concentration
- CL: clearance
- Vd: volume of distribution

- $t_{1/2}$: half-life
- K_{el} : elimination constant
- MRT: mean residence time

Bioanalytical measurement

- Circulating endothelial cells (CEC), vascular endothelial growth factor (VEGF) and circulating endothelial progenitor (CEP) cells
- Tumor micro vessel density and blood flow by dynamic contrast-enhanced MRI (DCE-MRI) at baseline and 6 hours after the infusion of the drug on C1D1
- Human Papillomavirus (HPV) status (expression of p16 by immunohistochemistry [IHC]) at baseline

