- Biomarkers analysis would be performed on patients enrolled in the run-in phase including circulating endothelial cells (CEC), vascular endothelial growth factor (VEGF) and circulating endothelial progenitor (CEP) cells
- Tumor micro vessel density and blood flow by dynamic contrast-enhanced MRI (DCE-MRI) will be performed in patients with identified sites which be selected by the sponsor at both baseline and 6 hours after the infusion of the drug on Cycle 1, Day 1. Analysis of DCE-MRI data might not be covered by this SAP.

Depending on the availability of biomarker data (CEC, VEGF and CEP), these data will be summarised descriptively by dose level and overall. These data will be listed as well for all subjects.

14. Handling of Missing Data

Missing values will not be imputed.

15. Changes to the Planned Analysis

Any changes to the analyses outlined in the approved SAP will be detailed in the Clinical Study Report (CSR).

16. Interim and Final Analysis

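### SAP 10.1 sets no earliest scan day for disease control, so stable disease seen after a Cycle 1 or 2 stop can be reported as Week-9 DCR

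*SAP*

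**What the plan says.** The endpoint is tied to Week 9 in three places.

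- Protocol synopsis, Endpoints: "complete response (CR) + partial response (PR) + stable disease (SD) at Week 9, according to RECIST v1.1 criteria".
- Protocol section 2.2, primary objective: "To assess the disease control rate (DCR) at the end of the 9th week".
- SAP section 2.3, on the subjects counted: they "have achieved complete response (CR), partial response (PR) and stable disease (SD) at Week 9 after first treatment, according to RECIST v1.1".

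SAP section 10.1 then gives the rule that will be programmed. It equates Week 9 with Cycle 4, Day 1, and the Week-9 evaluation "or end of treatment/early termination will be pooled and used as the best overall response from start of dosing up to Week 9". The same section says that the proportion and exact confidence intervals for "each of the response categories (CR, PR, SD, PD, and unevaluable) by dose level will also be presented", but it does not define the unevaluable category.

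The early scan comes from protocol section 3.4, which includes imaging in the end-of-treatment (EOT)/early-withdrawal visit. The EOT visit is 21 ± 2 days after the last infusion. For early withdrawal: "Early withdrawal visit should be conducted within 21 days after the patient receives the last dose of study treatment".

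Two general SAP conventions also bear on the table. Percentages default to "the denominator being the number of subjects in the relevant population with non-missing data, unless otherwise specified" (section 3), and "Missing values will not be imputed" (section 14).

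**The concern.** A response status at a fixed time and a best response over an interval are different quantities. Under the section 10.1 rule, a subject who stops in Cycle 1 or 2, has SD on the withdrawal scan and has no later scan counts as having disease control. Nothing was observed about that subject at Week 9. Neither document states an earliest qualifying day or a minimum duration of SD, and no rule sends an early SD reading to the unevaluable row.

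For such a subject the rule can raise the DCR or leave it unchanged; it cannot lower it. SAP Table 14.2.1.1 (tumour response and DCR) is marked to be generated, so the rule will be used. What is at stake is whether the reported figure means what its label says.

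**Working it through.** The plan gives no figure of its own for this point, so the check is calendar arithmetic from the visit schedule plus the exact interval named in SAP 10.1.

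**Inputs**
- Infusion days (protocol Table 1): C1D1 = Day 1 (± 0), C1D8 = Day 8 (± 1), C2D1 = Day 22 (± 1), C2D8 = Day 29 (± 1), C3D8 = Day 50 (± 1), C4D1 = Day 64 (± 1).
- Imaging within 5 days before the next cycle (protocol 3.2.11).
- Early-withdrawal visit within 21 days of the last dose; EOT visit at 21 ± 2 days (protocol 3.4).
- Five subjects enrolled (SAP 1); Clopper-Pearson intervals (SAP 10.1).

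**Earliest scheduled Week-9 scan.** Earliest C4D1 is 64 − 1 = 63, and 63 − 5 = Day 58.

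**Scan days after an early stop, no dose delay**
- Early withdrawal, latest day = latest infusion day + 21.
- EOT, earliest day = earliest infusion day + 19; latest day = latest infusion day + 23.
- Gap = 58 − scan day.

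| Last infusion | Early withdrawal: latest day | Smallest gap | EOT: days | Gap |
|---|---|---|---|---|
| C1D1 | 1 + 21 = 22 | 36 | 20 to 24 | 34 to 38 |
| C1D8 | 9 + 21 = 30 | 28 | 26 to 32 | 26 to 32 |
| C2D1 | 23 + 21 = 44 | 14 | 40 to 46 | 12 to 18 |
| C2D8 | 30 + 21 = 51 | 7 | 47 to 53 | 5 to 11 |

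The early-withdrawal column gives only the smallest gap, because protocol 3.4 sets no earliest day for that visit. A scan the day after C1D1 would be on Day 2, a gap of 58 − 2 = 56 days, or 8 weeks. The range is therefore 7 to about 56 days under the early-withdrawal rule and 5 to 38 days under the EOT rule.

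**Dose delay.** One 14-day hold (the limit in protocol 4.9) before C2D8 moves the latest scan after a C2D8 stop to 51 + 14 = Day 65, or 53 + 14 = Day 67 under the EOT rule. The deciding fact is therefore the scan day, not the cycle in which treatment stopped.

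**The upper end is loose too.** A subject who completes three cycles and does not continue has an EOT scan between 49 + 19 = Day 68 and 51 + 23 = Day 74. Whether up to Week 9 means Day 63 (9 × 7) or the latest C4D1 (Day 65), a literal reading excludes that legitimate scan.

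**Effect on the reported DCR.** With a denominator of 5, moving one subject from non-control to control changes x/5 to (x + 1)/5, which is +20 points. For x = 0:
- 0/5 = 0%: 95% CI 0–52.2%, 90% CI 0–45.1%.
- 1/5 = 20%: 95% CI 0.5–71.6%, 90% CI 1.0–65.7%.

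**The case against.** **The rule is disclosed and fits the evaluability criterion.** SAP 10.1 presents the pooling openly as a choice for this analysis. Protocol 8.5 makes a patient evaluable for DCR with a single on-study assessment and sets no minimum day. Both statements are true, but evaluability decides who is assessed, not when SD counts. SAP 2.3 keeps the Week-9 definition and 10.1 does not say that it changes the endpoint. Protocol 8.1 asks for significant analysis changes to be highlighted in the SAP; SAP section 4 does this for the analysis populations, whereas 10.1 does not do it for DCR.

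**RECIST v1.1 may supply a rule.** Both documents assign response by RECIST v1.1, which is not reproduced in them. The finding is therefore limited to what the two documents state.

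**Pooling is useful.** This stands in part. It captures early PD and the EOT scan of a three-cycle completer, so the remedy should keep both.

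**The consequence is small.** This stands. DCR is a Phase II objective and Phase II never opened. SAP section 1 puts the focus on safety, and section 10 makes efficacy descriptive. The tumour-response, drug-administration and early-discontinuation listings, all marked to be generated, allow a reader to check scan days.

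**Stronger readings that the documents do not support**
- A reader might infer that the rule inflates the type I error of the two-stage design. It could have done so in Phase II, but that test will not be run, and the documents give no rate of early SD from which to size the effect.
- A reader might infer that the DCR of this trial is overstated. Nothing shows that any of the five subjects had SD on an early scan with no Week-9 scan.
- A reader might infer that such a subject would otherwise drop out of the denominator as missing, under the default in SAP section 3. SAP 10.1 reports unevaluable as a category, so the more natural reading keeps the subject in the denominator. The 20-point figure uses that reading.

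**Conclusion.** The concern holds as an internal conflict of minor severity. SAP 10.1 as written allows SD from a scan taken 5 days to about 8 weeks before the earliest scheduled Week-9 scan to be reported under a Week-9 label. These gaps assume an undelayed schedule and a last infusion in Cycle 1 or 2. Each subject so reclassified adds 20 points to the overall DCR, assuming all five enrolled subjects are in the denominator and the subject would otherwise be non-control. Whether any subject is affected cannot be told from the documents. No hypothesis test or Phase II decision depends on the result, and with intervals as wide as 0.5–72% the table would carry little information in any case. The point concerns correct labelling of a descriptive figure and its comparability with the stated endpoint.

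**What to change.** Amend SAP 10.1 as follows.

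1. Count disease control only from a CR, PR or SD evaluation inside a stated Week-9 window defined by scan day from first dose: about Day 58 (earliest scheduled scan before C4D1) to Day 74 (latest scheduled EOT scan of a three-cycle completer). Extend the upper bound by the days of dose delay, which SAP section 8 already records. State an allowance for subjects who received all three cycles and were scanned slightly earlier. After a last infusion at C3D8 (Day 50 ± 1), an early-withdrawal scan can precede Day 58, and a hard lower bound would turn such a subject into a non-control.
2. Let scans before the window establish PD only.
3. Show subjects with no in-window evaluation and no earlier PD as unevaluable. Keep them in the FAS denominator as not having demonstrated disease control, and say that this overrides the non-missing default in SAP section 3. No response is imputed, so section 14 is respected.
4. Keep the pooled result only as a supportive line labelled *best response up to Week 9*, not as Week-9 DCR.

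The cost is one SAP paragraph, a window rule in the programming and one or two extra lines in Table 14.2.1.1. The reported DCR may be lower.
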